3.2 Exclusion Criteria

Participants who exhibit any of the following conditions at screening will not be eligible for admission into the study.

- SBRT target size >8 cm in maximum diameter (or >100 cc in volume)
- Hematologic malignancies (including lymphoma, multiple myeloma)
- Prior RT of greater dose intensity than 100 Gy₂ based on a biological effective dose (BED) calculation [BED (Gy2) = $nd \times (1+d/\alpha/\beta)$; where n=number of fractions, d=dose per fraction, $\alpha/\beta=2$]
- Epidural tumor <2 mm from spinal cord
- Requirement of active receipt of systemic therapies concurrent with SBRT (concurrent hormonal therapies are allowed)
- Inability to lie flat and still for treatment delivery despite anti-anxiety and/or pain medications
- Non-English speakers are excluded from this study due to use of questionnaires which have not been validated in other languages.
- Patients lacking the capacity to describe their symptoms are excluded as that precludes them (or anyone on their behalf) from filling out the validated questionnaires about symptoms/toxicity.
- Pregnant women are excluded from this study because radiotherapy has the potential for teratogenic or abortifacient effects.
- Individuals with a history of a different malignancy are ineligible **except** for the following circumstances: if they have been disease-free for at least 2 years and are deemed by the investigator to be at low risk for recurrence of that malignancy; or if diagnosed and treated within the past 2 years for cervical cancer *in situ* or basal cell or

squamous cell carcinoma of the skin.

3.3 Inclusion of Women and Minorities

Both men and women of all races and ethnic groups are eligible for this trial.

4. PRETREATMENT EVALUATIONS/MANAGEMENT

4.1 Table of acceptable time intervals of pretreatment assessments

Assessment	Acceptable time interval prior to initiation of SBRT (days)
History & physical exam	28
Performance status	28
Adverse event evaluation	28
Pregnancy test*	21
Radiologic evaluation	21
QOL questionnaire	28

* For pre-menopausal women for whom pregnancy is a possibility (i.e., have not undergone a hysterectomy)

4.2 Information regarding washout from prior therapies

For non-hormonal therapies, the study requires a wash out period of 3 half lives of the systemic agent. However it is also acceptable to begin sooner if there is agreement between the treating radiation oncologist and the medical oncologist based on discussion of data regarding particular biologic properties of the systemic agent, data regarding its safety when given with radiation therapy, and/or the needs of the patient.

5. REGISTRATION PROCEDURES

5.1 General Guidelines for DF/HCC Institutions

Institutions will register eligible participants in the Clinical Trials Management System (CTMS) OnCore. Registrations must occur prior to the initiation of protocol therapy. Any participant not registered to the protocol before protocol therapy begins will be considered ineligible and registration will be denied.

An investigator will confirm eligibility criteria and a member of the study team will complete the protocol-specific eligibility checklist.

Following registration, participants may begin protocol therapy. Issues that would cause

treatment delays should be discussed with the Overall Principal Investigator (PI). If a participant does not receive protocol therapy following registration, the participant's registration on the study must be canceled. Registration cancellations must be made in OnCore as soon as possible.

5.2 Registration Process for DF/HCC Institutions

DF/HCC Standard Operating Procedure for Human Subject Research Titled *Subject Protocol Registration* (SOP #: REGIST-101) must be followed.

5.3 General Guidelines for Other Investigative Sites

N/A

5.4 Registration Process for Other Investigative Sites

N/A

5.5 Criteria for Taking a Participant Off Protocol Therapy

Duration of therapy will depend on individual response, evidence of disease progression and tolerance. In the absence of treatment delays due to adverse event(s), treatment may continue as detailed in section 6.1 or until one of the following criteria applies:

- Disease progression
- Intercurrent illness that prevents further administration of treatment
- Unacceptable adverse event(s)
- Participant demonstrates an inability or unwillingness to comply with the treatment regimen and/or documentation requirements
- Participant decides to withdraw from the protocol therapy
- General or specific changes in the participant's condition render the participant unacceptable for further treatment in the judgment of the treating investigator

Participants will be removed from the protocol therapy when any of these criteria apply. The reason for removal from protocol therapy, and the date the participant was removed, must be documented in the case report form (CRF). Alternative care options will be discussed with the participant.

The research team updates the relevant Off Treatment/Off Study information in OnCore.

In the event of unusual or life-threatening complications, treating investigators must immediately notify the Overall PI, [name] at pager # [name].

5.6 Criteria for Taking a Participant Off Study

Participants will be removed from study when any of the following criteria apply:

- Lost to follow-up
- Withdrawal of consent for data submission
- Death

The reason for taking a participant off study, and the date the participant was removed, must be documented in REDCap.

The research team updates the relevant Off Treatment/Off Study information in OnCore.

6. RADIATION THERAPY

Protocol treatment must begin within 4 weeks after enrollment on the study.

6.1 Dose Specifications: SBRT

6.1.1 Prescription Dose: To be determined by the treating physician from the following previously employed regimens according to the clinical circumstances of each case (e.g. meeting normal-tissue constraints)

- Spine: 18 Gy x 1, 9 Gy x 3, or 6 Gy x 5
- Non-Spine Bone: 18Gy x 1, 9 Gy x 3 or 6 Gy x 5

6.1.2 Dose will be normalized such that at least 95% of the Planning Target Volume (PTV) receives the prescription dose and will be scored as per protocol. The minimum allowable dose within the PTV is >80% of the prescribed dose to a volume that is at least 1 cc.

6.1.3 Participants will be treated entirely via SBRT and shall receive prescription doses to the PTV (with the above constraints). All attempts should be made to deliver the PTV dose with the above heterogeneity constraints with adherence to the critical structure parameters listed below in Table 1.

See Section 6.5 below for specifics regarding when to implement a dose reduction.

6.1.4 In the retreatment of the spinal cord and/or cauda equina, BED calculations will be employed to ensure retreatment dose does not exceed $BED=140\text{ Gy2}$ (alpha/beta = 2). In retreatment to other normal tissues, the prior dose received to the organ(s) at risk will be taken into account together with dose constraints given in Table 1 to formulate final dose constraints tailored to each patient scenario.

6.2 Technical Factors

6.2.1 RT will be delivered with megavoltage equipment at energies $\geq 6\text{ MV}$.

6.2.2 All treatments will be delivered on a dedicated stereotactic linear accelerator that includes dedicated imaging and a robotic couch top. Imaging can include either live imaging with orthogonal kV beams as part of a CyberKnife Treatment Delivery System or onboard conebeam CT imaging and orthogonal 2D/3D matching.

6.3 EBRT Localization, Simulation, and Immobilization

Simulation will be CT-based in all cases. The use of intravenous or intrathecal contrast at the time of simulation is allowed at the discretion of the treating physician, but is generally not required. Participants will be positioned on a flat tabletop with a customized immobilization for stabilization and setup reproducibility. CT images should be acquired at a slice thickness of 1-1.25 mm. For rib lesions which may move with respiratory motion, a 4D CT or inspiration/expiration breath hold, will be utilized for target delineation. Target volumes (Section 6.4.1) and normal critical structures (Section 6.5) will be defined in the slices in which they are visualized. The treating radiation oncologist will review the fusion of the diagnostic MRI scan to the CT simulation scan, if applicable.

6.4 Treatment Planning/Target Volumes

6.4.1 The definition of volumes will be in accordance with the International Commission on Radiation Units and Measurements (ICRU) Report #50: Prescribing, Recording, and Reporting Photon Beam Therapy.

6.4.1.1 The gross tumor volume (GTV) is defined by the physician as all known disease as defined by the planning CT and any other diagnostic imaging obtained.

6.4.1.2 The clinical target volume (CTV) is the GTV plus areas considered to contain microscopic disease, delineated by the treating physician. This is optional at the treating radiation oncologist's discretion. This is in accordance with the International Spine Radiosurgery Consortium Consensus Guidelines for Target Volume Definition in Spinal Stereotactic Radiosurgery.¹⁷

6.4.1.3 The planning target volume (PTV) will provide a 0-2 mm margin around the CTV to compensate for the variability of treatment setup and internal organ motion. This is in accordance with the International Spine Radiosurgery Consortium Consensus Guidelines for Target Volume Definition in Spinal Stereotactic Radiosurgery.¹⁷

6.4.1.4 For conventional linac based SBRT, the ICRU reference points are to be located in the central part of the PTV and, secondly, on or near the central axis of the beams. Typically these points should be located on the beam axes or at the intersection of the beam axes.

6.4.1.5 Normal critical structures are to be defined on the treatment planning CT by the physician and/or treatment planner and will be based on the site being treated. Max doses are based on a point volume of 0.035 cc.

For example, for a thoracic spine metastasis around the level of the carina, the organs at risk would include:

- Heart
- Right lung, left lung, total lung
- Esophagus
- Bronchial structures
- Great vessels
- Spinal cord
- Skin

6.4.1.6 Volumetric modulated arc therapy (VMAT) or CyberKnife will be used to deliver conformal therapy to the entire PTV while limiting dose to critical structures as defined above.

6.5 Critical Structures

Critical structure dose constraints shall remain consistent with Table 1 above. While every effort should be made to deliver prescription doses to the PTV as specified while adhering to these constraints, it is recognized that certain anatomical factors may prevent this.

Excluding spinal cord and cauda equina, for purposes of compliance, up to a 5% absolute increase in the volume of a critical structure receiving greater than the specified dose will be considered “variation acceptable,” without a protocol deviation. Any increase in critical structure volume greater than 5% receiving more than the specified dose will be considered a “deviation unacceptable”. For spinal cord and cauda equina, any dose higher than stated in Table 1 will be considered “deviation unacceptable”. It is at this point that a dose reduction should be considered.

Table 1. Critical Structure Dose Constraints (from Benedict et al.¹⁸)

Serial tissue	Max critical volume above threshold	One fraction			Three fractions			Five fractions		
		Threshold dose (Gy)	Max point dose (Gy) ^a	Threshold dose (Gy)	Max point dose (Gy) ^a	Threshold dose (Gy)	Max point dose (Gy) ^a	Threshold dose (Gy)	Max point dose (Gy) ^a	End point (≥Grade 3)
Optic pathway	<0.2 cc	8	10	15.3 (5.1 Gy/fx)	17.4 (5.8 Gy/fx)	23 (4.6 Gy/fx)	25 (5 Gy/fx)	Neuritis Hearing loss		
Cochlea			9		17.1 (5.7 Gy/fx)			Neuritis Hearing loss		
Brainstem (not medulla)	<0.5 cc	10	15	18 (6 Gy/fx)	23.1 (7.7 Gy/fx)	23 (4.6 Gy/fx)	31 (6.2 Gy/fx)	Cranial neuropathy		
Spinal cord and medulla	<0.35 cc	10	14	18 (6 Gy/fx)	21.9 (7.3 Gy/fx)	23 (4.6 Gy/fx)	30 (6 Gy/fx)	Myelitis		
Spinal cord subvolume (5–6 mm above and below level treated per Ryu)	<1.2 cc	7	12.3	12.3 (4.1 Gy/fx)			14.5 (2.9 Gy/fx)	Myelitis Neuritis		
<10% of subvolume					18 (6 Gy/fx)	21.9 (7.3 Gy/fx)	23 (4.6 Gy/fx)	Myelitis Neuritis		
Cauda equina	<5 cc	10	14	21.9 (7.3 Gy/fx)	24 (8 Gy/fx)	30 (6 Gy/fx)	32 (6.4 Gy/fx)	Neuropathy		
Sacral plexus	<5 cc	14	16	22.5 (7.5 Gy/fx)	24 (8 Gy/fx)	30 (6 Gy/fx)	32 (6.4 Gy/fx)	Stenosis/fistula		
Esophagus ^b	<5 cc	11.9	15.4	17.7 (5.9 Gy/fx)	25.2 (8.4 Gy/fx)	19.5 (3.9 Gy/fx)	35 (7 Gy/fx)	Neuropathy		
Brachial plexus	<3 cc	14	17.5	20.4 (6.8 Gy/fx)	24 (8 Gy/fx)	27 (5.4 Gy/fx)	30.5 (6.1 Gy/fx)	Pericarditis		
Heart/epicardium	<15 cc	16	22	24 (8 Gy/fx)	30 (10 Gy/fx)	32 (6.4 Gy/fx)	38 (7.6 Gy/fx)	Aneurysm		
Great vessels	<10 cc	31	37	39 (13 Gy/fx)	45 (15 Gy/fx)	47 (9.4 Gy/fx)	53 (10.6 Gy/fx)	Stenosis/fistula Stenosis with atherosclerosis Pain or Fracture		
Trachea and large bronchi ^b	<4 cc	10.5	20.2	15 (5 Gy/fx)	30 (10 Gy/fx)	16.5 (3.3 Gy/fx)	40 (8 Gy/fx)	Stenosis/fistula Stenosis with atherosclerosis Pain or Fracture		
Bronchus-smaller airways	<0.5 cc	12.4	13.3	18.9 (6.3 Gy/fx)	23.1 (7.7 Gy/fx)	21 (4.2 Gy/fx)	33 (6.6 Gy/fx)	Stenosis/fistula Stenosis with atherosclerosis Pain or Fracture		
Rib	<1 cc	22	30	28.8 (9.6 Gy/fx)	36.9 (12.3 Gy/fx)	35 (7 Gy/fx)	43 (8.6 Gy/fx)	Stenosis/fistula Stenosis with atherosclerosis Pain or Fracture		
<30 cc				30 (10.0 Gy/fx)				Stenosis/fistula Stenosis with atherosclerosis Pain or Fracture		
Skin	<10 cc	23	26	30 (10.5 Gy/fx)	33 (11 Gy/fx)	36.5 (7.3 Gy/fx)	39.5 (7.9 Gy/fx)	Ulceration/fistula		
Stomach	<10 cc	11.2	12.4	16.5 (5.5 Gy/fx)	22.2 (7.4 Gy/fx)	18 (3.6 Gy/fx)	32 (6.4 Gy/fx)	Ulceration/fistula		
Duodenum ^b	<5 cc	11.2	12.4	16.5 (5.5 Gy/fx)	22.2 (7.4 Gy/fx)	18 (3.6 Gy/fx)	32 (6.4 Gy/fx)	Ulceration/fistula		
<10 cc		9	11.4	11.4 (3.8 Gy/fx)		12.5 (2.5 Gy/fx)		Ulceration/fistula		
Jejunum/ileum ^b	<5 cc	11.9	15.4	17.7 (5.9 Gy/fx)	25.2 (8.4 Gy/fx)	19.5 (3.9 Gy/fx)	35 (7 Gy/fx)	Entertitis/obstruction		
Colon ^b	<20 cc	14.3	18.4	24 (8 Gy/fx)	28.2 (9.4 Gy/fx)	25 (5 Gy/fx)	38 (7.6 Gy/fx)	Colitis/fistula		
Rectum ^b	<20 cc	14.3	18.4	24 (8 Gy/fx)	28.2 (9.4 Gy/fx)	25 (5 Gy/fx)	38 (7.6 Gy/fx)	Proctitis/fistula		
Bladder wall	<15 cc	11.4	18.4	16.8 (5.6 Gy/fx)	28.2 (9.4 Gy/fx)	18.3 (3.65 Gy/fx)	38 (7.6 Gy/fx)	Cystitis/fistula		
Penile bulb	<3 cc	14	34	21.9 (7.3 Gy/fx)	42 (14 Gy/fx)	30 (6 Gy/fx)	50 (10 Gy/fx)	Impotence		
Femoral heads (right and left)	<10 cc	14			21.9 (7.3 Gy/fx)	30 (6 Gy/fx)		Necrosis		
Renal hilum/vascular trunk	<2/3 volume	200 cc	10.6	18.6 (6.2 Gy/fx)			23 (4.6 Gy/fx)	Malignant hypertension		
Minimum critical volume below threshold				One fraction			Three fractions			
Parallel tissue				Threshold dose (Gy)	Max point dose (Gy) ^a	Threshold dose (Gy)	Max point dose (Gy) ^a	Threshold dose (Gy)	Max point dose (Gy) ^a	End point (≥Grade 3)
Lung (right and left)	1500 cc	7	NA-Parallel tissue	11.6 (2.9 Gy/fx)	NA-Parallel tissue	12.5 (2.5 Gy/fx)	NA-Parallel tissue	13.5 (2.7 Gy/fx)	NA-Parallel tissue	Basic lung function
Lung (right and left)	1000 cc	7.4	NA-Parallel tissue	12.4 (3.1 Gy/fx)	NA-Parallel tissue	14.2 (4.8 Gy/fx)	NA-Parallel tissue	21 (4.2 Gy/fx)	NA-Parallel tissue	Pneumonitis
Liver	700 cc	9.1	NA-Parallel tissue	19.2 (4.8 Gy/fx)	NA-Parallel tissue					Basic liver function
Renal cortex (right and left)	200 cc	8.4	NA-Parallel tissue	16 (4 Gy/fx)	NA-Parallel tissue	17.5 (3.5 Gy/fx)	NA-Parallel tissue			Basic renal function

^aPoint[®] defined as 0.035 cc or less.^bAvoid circumferential irradiation.

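### Four parallel-tissue limits in Table 1 (lung 1500 cc, lung 1000 cc, liver, renal cortex) print a total exactly four times the per-fraction dose, so none is a self-consistent limit for 9 Gy x 3

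*Combined protocol and SAP*

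**What the plan says.** Section 6.1.1 offers the same three schedules for both kinds of target: "Spine: 18 Gy x 1, 9 Gy x 3, or 6 Gy x 5" and "Non-Spine Bone: 18Gy x 1, 9 Gy x 3 or 6 Gy x 5". Table 1 is likewise headed one, three and five fractions. Neither place mentions a four-fraction schedule.

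Section 6.5 makes Table 1 the working standard: "Critical structure dose constraints shall remain consistent with Table 1 above". For organs other than spinal cord and cauda equina, up to 5% extra volume above the limit is tolerated. Beyond that, "Any increase in critical structure volume greater than 5% receiving more than the specified dose will be considered a" deviation classed as unacceptable, and a dose reduction is to be considered. Section 6.1.4 also draws on Table 1 when limits are set for re-irradiation of normal tissues other than cord and cauda equina.

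The parallel-tissue part of Table 1, under "Minimum critical volume below threshold", gives each organ a volume to be spared and a threshold dose. After the one-fraction value, the next cell reads:

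- lung, 1500 cc: 11.6 Gy (2.9 Gy/fx)
- lung, 1000 cc: 12.4 Gy (3.1 Gy/fx)
- liver, 700 cc: 19.2 Gy (4.8 Gy/fx)
- renal cortex, 200 cc: 16 Gy (4 Gy/fx)

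Section 6.4.1.5 lists "Right lung, left lung, total lung" among the organs at risk in its thoracic spine example.

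**The concern.** A cell that gives a total and a per-fraction dose fixes a number of fractions. In these four cells that number is four, which the protocol does not use. A planner working from the total and one working from the bracket would hold the same 9 Gy x 3 plan to different limits, and the compliance review in Section 6.5 would have no basis for preferring either.

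What is at stake is the sparing of lung, liver and kidney in three-fraction plans, and how those plans are scored. If the total is the wrong figure, the error is on the permissive side.

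**Working it through.** **Inputs.** The four cells above, and the one- and five-fraction cells of the same rows (Table 1); the allowed schedules (Section 6.1.1); the BED formula (Section 3.2).

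**Step 1: implied fractions = total / per-fraction dose.**

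- 11.6 / 2.9 = 4.00
- 12.4 / 3.1 = 4.00
- 19.2 / 4.8 = 4.00
- 16 / 4 = 4.00

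**Step 2: compare with the allowed schedules.**

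| Organ | Printed total (Gy) | 3 x bracket (Gy) | Gap (Gy) | 5 x bracket (Gy) | Total / 3 (Gy/fx) |
|---|---|---|---|---|---|
| Lung 1500 cc | 11.6 | 8.7 | 2.9 | 14.5 | 3.87 |
| Lung 1000 cc | 12.4 | 9.3 | 3.1 | 15.5 | 4.13 |
| Liver | 19.2 | 14.4 | 4.8 | 24 | 6.40 |
| Renal cortex | 16 | 12 | 4.0 | 20 | 5.33 |

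The cells fail at three and at five fractions. Against three times the bracket, each total is higher by 4/3 - 1 = 33.3%.

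**Step 3: control on the rest of the table.** Of the 93 serial-tissue cells that give a total with a per-fraction dose, 47 match three fractions and 45 match five, within 0.05 Gy. One matches neither: skin, 30 (10.5). Of the nine parallel-tissue cells, four match five fractions (12.5/2.5, 13.5/2.7, 21/4.2 and 17.5/3.5), four match only four fractions (the disputed cells), and one in the lung 1000 cc row, 14.2 (4.8), matches no whole number. The skin cell and the 14.2 cell are not relied on.

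**Step 4: is the total plausible as a three-fraction limit?** With BED = nd x (1 + d/(alpha/beta)), compare it with the same row's one- and five-fraction limits. The documents give no alpha/beta for lung or kidney, so 2, 3, 4 and 10 are assumed. At 3:

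- Lung 1500 cc: one fraction, 7 x (1 + 7/3) = 23.3. Five fractions, 12.5 x (1 + 2.5/3) = 22.9. Printed total in three, 11.6 x (1 + 3.867/3) = 26.6; in four, 11.6 x (1 + 2.9/3) = 22.8. Three times the bracket, 8.7 x (1 + 2.9/3) = 17.1.
- Renal cortex: one fraction, 8.4 x (1 + 8.4/3) = 31.9. Five fractions, 17.5 x (1 + 3.5/3) = 37.9. Printed total in three, 16 x (1 + 5.333/3) = 44.4; in four, 16 x (1 + 4/3) = 37.3. Three times the bracket, 12 x (1 + 4/3) = 28.0.

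The same formula at the ends of the assumed range:

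| Row | alpha/beta | One fraction | Five fractions | Total in three | 3 x bracket |
|---|---|---|---|---|---|
| Lung 1500 cc | 2 | 31.5 | 28.1 | 34.0 | 21.3 |
| Lung 1500 cc | 10 | 11.9 | 15.6 | 16.1 | 11.2 |
| Renal cortex | 2 | 43.7 | 48.1 | 58.7 | 36.0 |
| Renal cortex | 10 | 15.5 | 23.6 | 24.5 | 16.8 |

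At all four values the printed total, given in three fractions, has a higher BED than both neighbouring limits. Three times the bracket is below both at 2 to 4, but for renal cortex at 10 it lies between them.

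One caveat applies to lung 1500 cc. As read, that row holds two cells that fit five fractions, and 12.5 was taken because it comes next in order. With 13.5 instead, the five-fraction BED at alpha/beta 3 is 13.5 x (1 + 2.7/3) = 25.7, still below 26.6. At 10 it is 13.5 x 1.27 = 17.1, above 16.1. The lung comparison at 10 therefore depends on that choice. Liver has no readable five-fraction cell and the lung 1000 cc row is too damaged to use, so neither was compared.

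**The case against.** The strongest reply is that these cells lie in the worst-read part of the table. The header has slipped, no five-fraction heading survives there, the lung rows carry an extra threshold and the liver row lacks one. The original page was not seen, and the three-fraction position is inferred. That much stands, and it is why the first step of the fix is to look at the page. It does not remove the contradiction. Total and bracket share one cell, so a shifted column cannot part them; a ratio of four fits no column wherever the cell belongs; and four exact ratios of 4.00 are hard to put down to misread digits.

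The second reply is that the column is headed as a threshold dose in Gy, so the total governs and the bracket is only a restatement. The heading does favour the total. It shows which figure a planner would probably use, but not that the figure is a valid three-fraction limit, and Step 4 gives reason to doubt that for two of the rows.

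The third reply is that the table is credited to a cited report and may have been copied faithfully. That cannot be checked here, and a faithful copy would still leave this protocol's limit undefined.

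The reach is small: only 9 Gy x 3 plans near lung, liver or kidney can be affected, and Section 6.7.2.1 also asks the physician to weigh the tolerance of each structure.

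**Conclusion.** The point holds. None of the four cells is a self-consistent limit for 9 Gy x 3, and the two readings of each differ by 2.9 to 4.8 Gy (33%). A third possibility fits the exact ratio best: the whole cell is a four-fraction limit placed under three fractions. Then the printed total is too loose for three fractions and three times the bracket may be too tight, so neither number can be presumed right. The BED comparison supports this for lung 1500 cc and renal cortex only, under assumed alpha/beta values; it does not prove it. The sizes given rest on the inferred three-fraction position, whereas the contradiction does not.

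A reader might infer that the true limits are 8.7, 9.3, 14.4 and 12 Gy, or that patients received too much dose to lung, liver or kidney. The documents support neither. They do not say which figure is wrong, and they show no plan whose compliance status would change. The sample size, the 6-month local control endpoint and the primary analysis are untouched. The point still deserves correction, because Section 6.5 scores plans against these figures.

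**What to change.** 1. Check the four cells against the original page of Table 1 and against the table's source. Replace each with one verified three-fraction total and a per-fraction dose equal to a third of it. Do not assume that either printed number is right.
2. Until that is done, apply three times the printed per-fraction dose (8.7, 9.3, 14.4 and 12 Gy), or have the investigator set and record the limit for each 9 Gy x 3 plan near lung, liver or kidney.
3. If a verified total is below the printed one, re-check the stored 9 Gy x 3 plans whose spared volume (1500, 1000, 700 or 200 cc) meets the printed total but not the verified one. If it is not below, no stored plan needs re-checking on this account.

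The cost is a clarification of four cells and, at most, a limited review of stored plans. Sample size, visits and the primary analysis do not change.

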1.1.3 Re-irradiation

Many anatomic structures have maximum cumulative tolerable doses; higher doses can cause severe toxicity. Re-irradiation, particularly in the spine, presents technical challenges due to safety concerns in re-irradiating normal tissues. The spinal cord has a tolerance that, if exceeded, can lead to cord myelopathy and/or spinal nerve radiculopathy¹⁰ causing significant morbidity. SBRT allows high doses to be given in a highly conformal nature, minimizing dose to the spinal cord while still allowing the tumor to receive a high dose of radiation. A publication from Beth Israel Hospital reported their use of SBRT for re-irradiation of epidural spinal metastases. In patients with a local recurrence who were previously treated with EBRT (3 Gy x 10), SBRT was given (either 8 Gy x 3 if the tumor did not touch spinal cord or 5-6 Gy x 5 when tumor abutted the cord). They reported very low toxicity (40% grade 1 fatigue and 20% grade 2 nausea), adequate pain relief (65%), and good local control (93% of the patients had stable or improved disease).¹¹

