6.7.2 Compliance Criteria

Cases which meet criteria as stated in Section 6.1.2 will be scored as per protocol.

The minimum allowable dose within the PTV is >80% of the prescribed dose to a volume that is at least 1 cc. Cases in which this small volume of at least 1 cc receives a minimum dose that is <80% but >75% will be scored as a “deviation acceptable”.

Cases in which 1 cc receives less than 75% of the prescribed dose will be scored as a “deviation unacceptable”. However, if this is what is required to keep the spinal cord or cauda equina within the maximum dose constraint, as specified above, this variation is considered “deviation acceptable”.

6.7.2.1 Acceptable dose heterogeneity will be as follows: The maximum dose volume of the PTV must not be shared by a normal critical structure. (Section 6.4.1.5). The maximum point dose to normal critical structures outside the PTV including the unspecified tissue should not exceed dose specified in Table 1. The treating physician must carefully consider the tolerance dose/volume to each critical normal structure and unspecified tissue.

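### The 140 Gy2 retreatment cap for cord and cauda equina (6.1.4) should be worded as cumulative and scored in 6.5; as written it adds nothing to Table 1

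*Combined protocol and SAP*

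**What the plan says.** Section 6.1.4 has two retreatment rules. For the cord and cauda equina: "In the retreatment of the spinal cord and/or cauda equina, BED calculations will be employed to ensure retreatment dose does not exceed" a BED of 140 Gy2, with alpha/beta = 2. For everything else: "In retreatment to other normal tissues, the prior dose received to the organ(s) at risk will be taken into account", together with Table 1, to set limits for each patient. Only the second rule mentions prior dose.

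For when to reduce dose, section 6.1.3 is followed by a pointer to 6.5. There, "For spinal cord and cauda equina, any dose higher than stated in Table 1 will be considered" an unacceptable deviation, and "It is at this point that a dose reduction should be considered". Section 6.5 does not mention the 140 Gy2 limit.

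Section 6.7.2.1 also uses Table 1 as the maximum for critical structures. Section 6.7.2 treats a PTV underdose below 75% in 1 cc as acceptable "if this is what is required to keep the spinal cord or cauda equina within the maximum dose constraint".

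Two other places bear on what was intended. Section 1.1.3 says "Many anatomic structures have maximum cumulative tolerable doses; higher doses can cause severe toxicity" and gives the cord as the example. Section 3.2 makes "Prior RT of greater dose intensity than 100" Gy2 an exclusion, calculated with the same alpha/beta of 2.

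**The concern.** A retreatment limit for the cord is useful only if it can be stricter than the limit that applies to every patient. Taken literally, 6.1.4 caps the new course alone, at a level above anything Table 1 allows. Table 1 has no term for prior dose, so on the literal wording no numeric cord limit in planning depends on what the cord has already received.

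If the cap is cumulative, as seems likely, a different gap appears. The section that decides what is a deviation, and when to consider lowering the dose, never refers to the cap. A plan could exceed it and still score as compliant.

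This bears mainly on cohort 2, which sections 2.1 and 13.1 define as re-irradiation of spinal disease, with 50 patients planned. Section 6.9.2 lists cord and nerve damage among late, permanent reactions, so the planning limit matters more than later toxicity review. The cord limit also decides when PTV underdose is excused under 6.7.2. If that constraint is taken to be Table 1, a plan that underdoses the target to respect a cumulative cap might not qualify for the allowance.

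**Working it through.** **Inputs.** BED formula and alpha/beta = 2 (3.2, 6.1.4); cap 140 Gy2 (6.1.4); prior-dose limit 100 Gy2 (3.2); 1, 3 or 5 fractions (6.1.1); Table 1 point maxima as printed; 3 Gy x 10 as an example prior course (1.1.3). The 140 Gy2 is a stated limit, so there is no derived figure to reproduce.

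**Step 1: Table 1 maxima on the BED scale.** For total dose D in n fractions, BED = D x (1 + (D/n)/2).

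| Organ | 1 fraction | 3 fractions | 5 fractions |
|---|---|---|---|
| Cord | 14 x (1 + 7) = 112.0 | 21.9 x (1 + 3.65) = 101.8 | 30 x (1 + 3) = 120.0 |
| Cauda equina | 14 x (1 + 7) = 112.0 | 24 x (1 + 4) = 120.0 | 32 x (1 + 3.2) = 134.4 |

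All six are below 140.

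**Step 2: what the cap alone would allow.** Solving for dose at BED X gives D = -n + sqrt(n² + 2nX). With X = 140, D = 15.8, 26.1 and 32.7 Gy in 1, 3 and 5 fractions. Each exceeds the Table 1 maximum for both organs, so the literal cap never binds on a plan that meets Table 1.

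**Step 3: what a cumulative cap would allow.** Assume the same cord point received the full prior dose and there is no recovery. Then X = 140 minus prior BED. Prior 3 Gy x 10 is 30 x (1 + 1.5) = 75 Gy2, leaving 65. A prior 8 Gy x 1, which is my assumption for the low end, is 8 x (1 + 4) = 40 Gy2, leaving 100. The 3.2 limit leaves 40.

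| Prior BED (Gy2) | 1 fraction (Gy) | 3 fractions (Gy) | 5 fractions (Gy) |
|---|---|---|---|
| Table 1 cord maximum | 14 | 21.9 | 30 |
| 40 | 13.2 | 21.7 | 27.0 |
| 75 | 10.4 | 17.0 | 21.0 |
| 100 | 8.0 | 12.8 | 15.6 |

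After 75 Gy2 the gap from Table 1 is 3.6, 4.9 and 9.0 Gy. Table 1 is the stricter cord limit only if prior cord dose is below 140 - 112.0 = 28.0, 140 - 101.8 = 38.2 or 140 - 120.0 = 20.0 Gy2.

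**Step 4: cumulative BED at the Table 1 cord maximum.** Prior 75: 187.0, 176.8 and 195.0 Gy2. Prior 100: 212.0, 201.8 and 220.0 Gy2. Section 6.5 would flag none of these.

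**Step 5: how much cord is involved.** The maxima apply to a 0.035 cc point. Table 1 also holds the cord volume above 10, 18 and 23 Gy to less than 0.35 cc. Those thresholds are 60.0, 72.0 and 75.9 Gy2; with prior 75 they give 135.0, 147.0 and 150.9 Gy2. Outside that small volume, the excess over 140 after 3 Gy x 10 is therefore at most 0, 7.0 and 10.9 Gy2. At prior 100 the sums are 160.0, 172.0 and 175.9 Gy2.

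**The case against.** The strongest reply is that 6.1.4 is already cumulative in substance. Table 1 gives limits by fraction number, so a single course needs no BED conversion; BED is needed to add courses of different fractionation. The 100 Gy2 exclusion is on the same scale and fits as a prior limit beneath a 140 Gy2 total. Section 1.1.3 speaks of cumulative tolerance. A reading that leaves a safety rule with no effect is the weaker one. The contrast with other tissues also has an innocent explanation: cord and cauda equina get a fixed number, other organs get case-by-case limits. I accept all of this. It settles the probable intent, but not the wording of 6.1.4 or the missing link in 6.5.

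A reader might infer from 6.5 that prior cord dose is deliberately left out. The documents do not support that. Section 6.5 is silent on prior dose for every organ, including those for which 6.1.4 expressly counts it, and nothing in 6.5 cancels 6.1.4.

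Other safeguards exist: the prior-dose exclusion and the exclusion of epidural tumor within 2 mm of the cord (3.2), the physician's duty to weigh tolerance (6.7.2.1), and ongoing plan review (6.8). No other investigative sites are planned (5.3, 5.4), which lowers the chance of divergent practice. These reduce the risk, but none states a cumulative cord limit.

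Table 1 is visibly disordered in the extracted text. If the single-fraction cauda equina maximum were 16 Gy rather than the printed 14, its BED would be 16 x (1 + 8) = 144 Gy2 and the literal cap would bind in that one cell, by about 0.2 Gy. The cord results would not change.

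**Conclusion.** The point holds as a wording and scoring gap that should be closed. Read literally, the 140 Gy2 limit adds nothing for a plan that meets Table 1. Read cumulatively, which the context favours, it is stricter than Table 1 for prior cord doses above roughly 20 to 38 Gy2, yet 6.5 would not flag a breach. After 3 Gy x 10, a plan at the Table 1 cord maximum reaches 177 to 195 Gy2.

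These figures assume full overlap at one cord point, no recovery between courses, and a plan at the point maximum. They are worst-case point doses, and a reader should not take the 3.6 to 9.0 Gy gaps as typical of the treated cord, because the 0.35 cc volume limits also apply.

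Nor do the documents show that patients were or would be overdosed, or that local control is affected. The 50 planned for cohort 2 is an upper bound on those exposed there: section 3.1 asks only for prior radiation in the current area, and the number with prior cord dose at the treated level is not given.

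**What to change.** In 6.1.4, apply the 140 Gy2 limit to the sum of prior and retreatment BED at the spinal cord or cauda equina, in place of the retreatment dose. In 6.5, state that for retreated patients the scored limit for these organs is the lower of Table 1 and the dose that keeps that sum at or below 140 Gy2, and that the dose-reduction trigger follows it. Have 6.7.2 and 6.7.2.1 refer to the same limit, so that PTV underdose needed to meet it is scored consistently. No new dose value is proposed.

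The cost is two clauses and their cross-references. The clinical downside is somewhat more PTV underdose near the cord in some cohort 2 plans, which could lower control there; the documents give no basis for sizing that. Sample size and analysis do not change.
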